#### **Potential bias:**

-selection bias: Patients are recruited from an NYC based dermatology office. Patients must have the means to pay for the treatment as it is not covered by insurance (although prices may be discounted or negotiated, and free treatment may be offered, on a case to case bases depending on available resources and patient needs)

-risk of attrition bias if patients do not follow up or drop out of the study

-reporting bias: part of this study requires patients to complete a 5 night course of ointment application. We are trusting that the patient is completing and accurately reporting this in accordance with our detailed instructions provided.

**Data source:** Collected by [name] or by his medical assistants and inputted into Macpractice electronic medical record.

**Outcomes of interest:**

**primary**

1. Successful cure with the experimental method on all participants  
vs. clinical recurrence or worsening

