**secondary**

1. The experimental method successfully treats one type of cancer but not the other (BCCs but not SCCs or vice versa)
2. The experimental method successfully treats early stages of the cancers, but not later stages (ex. Treats superficial SCCs but not invasive SCCs)
3. The experimental method successfully treats only specific parts of the body (ex. Treats areas of the body with thinner skin like the face, but not areas of thicker skin like on the back.)
4. The experimental trial method successfully treats only certain patients (differing results depending on age, skin type, ethnicity, etc).

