**Statistics**

-Subgroups will be defined by cancer type, cancer invasiveness, skin type, and gender

- The sample size is likely to be 20-100 participants as estimated by the established patients at the office of [name] MD and the frequency of carcinoma diagnosis.
- On a per-case basis, treatment is considered effective if there is no clinical/histological recurrence in 5 years.
- For the study as a whole, the treatment is considered effective if the recurrence rate is lower or approximately equal to the comparison groups: other FDA approved/traditional treatment options. For example, studies have shown that after surgical excision, over 5 years, superficial BCC recurrence rate is between 2% and 5%, nodular BCC 2-8%, SCC in situ ~0.8%, and invasive SCC between 1.7% and 6.4%. And, most surgical excision recurrences occur within 2 years. Other methods such as electrodessication and curettage have higher recurrence rates. So, we would consider our treatment successful if our recurrence rates are lower or approximately equal to any of the approved treatment options.
- Treatment is not randomized. Participation is determined by the patient's willingness to participate. If they participate they are given the treatment. No placebos or control groups.

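### The primary outcome can be read as requiring zero recurrences, whereas the Statistics section judges the study by a recurrence rate and counts different events

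*Protocol*

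**What the plan says.** Under Outcomes of interest, the protocol lists one primary outcome: "Successful cure with the experimental method on all participants", followed by "vs. clinical recurrence or worsening". It gives no proportion and no time point there, and does not define cure.

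The four secondary outcomes are also worded as verdicts. Each describes success in only part of the population: one cancer type, earlier stages, some body sites, or some patients ("The experimental trial method successfully treats only certain patients").

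The Statistics section works at two levels. For a single case, "treatment is considered effective if there is no clinical/histological recurrence in 5 years". For the whole study, "the treatment is considered effective if the recurrence rate is lower or approximately equal to the comparison groups", restated as "we would consider our treatment successful if our recurrence rates are lower or approximately equal to any of the approved treatment options". It cites 5-year recurrence after excision of 2–5% for superficial BCC, 2–8% for nodular BCC, about 0.8% for SCC in situ and 1.7–6.4% for invasive SCC. The expected sample is 20 to 100 participants. The section does not refer back to the primary outcome.

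**The concern.** Taken word for word, the primary outcome tolerates no recurrence, while the study-level rule tolerates a non-zero rate. The secondary outcomes make the literal reading a fair one, because they look like the partial-success alternatives to cure in everyone. The background section reports the earlier work in the same terms, as complete clearance in every subject.

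Two things are at stake. First, a zero-recurrence target becomes harder to meet as the trial recruits more people, for reasons unrelated to how well the treatment works. Secondly, the study is uncontrolled and meant for publication, so readers need to know in advance which statement the result will be held to.

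The event definitions also differ. The primary outcome names clinical recurrence or worsening. Statistics names clinical or histological recurrence and leaves out worsening. Follow-up biopsies depend on patient consent (Schedule of events/visits). A site that looks clear but has a positive biopsy is therefore a recurrence under Statistics, and the primary outcome does not say where it belongs.

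**Working it through.** The protocol has no calculation to reproduce here. The 20–100 participants are a recruitment estimate, not derived from a power, margin or effect size.

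**Inputs.** Sample size n from 20 to 100, and true recurrence p set at the ends of the excision ranges; both are from Statistics. Assumptions: one lesion per participant, independent outcomes, complete 5-year follow-up, and a treatment exactly equal to excision.

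**Step 1: chance of missing the literal primary outcome.** P(at least one recurrence) = 1 − (1 − p)^n.

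- p = 5%: 1 − 0.95^20 = 1 − 0.358 = 64%; 1 − 0.95^100 = 1 − 0.006 = 99%.
- p = 2%: 1 − 0.98^20 = 1 − 0.668 = 33%; 1 − 0.98^100 = 1 − 0.133 = 87%.

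| True recurrence | n=20 | n=40 | n=60 | n=100 | Smallest n with a miss at least as likely as not |
|---|---|---|---|---|---|
| 0.8% (SCC in situ) | 15% | 27% | 38% | 55% | 87 |
| 1.7% (invasive SCC, low) | 29% | 50% | 64% | 82% | 41 |
| 2% (BCC, low) | 33% | 55% | 70% | 87% | 35 |
| 5% (superficial BCC, high) | 64% | 87% | 95% | 99% | 14 |
| 6.4% (invasive SCC, high) | 73% | 93% | 98% | 99.9% | 11 |
| 8% (nodular BCC, high) | 81% | 96% | 99% | >99.9% | 9 |

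**Step 2: chance of missing the literal outcome and still passing the study-level rule.** The protocol gives no margin for approximate equality, so passing needs an assumed cap on the observed rate. With m = n × cap rounded down, the joint probability is P(1 ≤ recurrences ≤ m).

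| Assumed cap | True recurrence | n=20 (m=1) | n=60 | n=100 |
|---|---|---|---|---|
| 5% (m=3 at n=60, 5 at n=100) | 2% | 27% | 67% | 85% |
| 5% | 5% | 38% | 60% | 61% |
| 8% (m=4 at n=60, 8 at n=100) | 2% | 27% | 70% | 87% |
| 8% | 5% | 38% | 77% | 93% |
| 8% | 8% | 33% | 46% | 59% |

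At n=20 no combination of a quoted rate with a cap of 5%, 6.4% or 8% exceeds about 38%. Under a strict cap of 0.8%, even one recurrence in 100 (1%) fails, so both statements demand zero and the joint probability is nil. The rule also admits any approved option, and the protocol says that some have higher recurrence than excision without giving a figure. A looser comparator would push the joint probability up towards the Step 1 figures.

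**The case against.** The strongest reply is that there is no conflict. The second half of the primary outcome makes it a two-category result, cure against recurrence or worsening, and the mention of all participants may only mean the whole cohort as opposed to subgroups. The data collection section records recurrence or no recurrence at each visit, and Statistics judges each case in the same way. Statistics also supplies the 5-year time point and the rate, and it is the only place that states when the study as a whole counts as effective. The fourth secondary outcome is explained as differing results by age, skin type and ethnicity, which suggests variation and not a verdict.

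Much of this stands. The per-participant reading is available and removes the contradiction. It does not settle the matter, because nothing in the protocol selects that reading, and the mismatch between clinical and histological events remains under either one.

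A reader might go further and infer that a treatment equal to excision would usually fail the primary outcome and pass the success rule. The documents do not support that across the planned range. At n=20 and 2% true recurrence, the literal outcome is met in 67% of trials. For SCC in situ, a miss is less likely than not until n=87. Passing the rule cannot be computed at all without a margin.

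**Conclusion.** The primary outcome is ambiguous. Read literally, it sets a zero-recurrence standard that the study-level rule does not share, and under either reading its event definition differs from the one in Statistics. On the literal reading, an excision-equal treatment misses the primary outcome in 15% to 81% of trials at n=20 and in 55% to over 99.9% at n=100, depending on which quoted excision rate is true. So a miss is frequent, and it is the usual result only in larger samples or at the higher rates.

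The figures rest on the assumptions listed with the inputs. Several lesions per participant would raise the chance of at least one recurrence; recurrences unseen because of drop-out would lower the observed count.

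It would be too much to say that the protocol contains two formal decision rules giving opposite answers. Only Statistics states a study-level criterion, and the primary outcome conflicts with it under one of two tenable readings. A sponsor should correct this before results accrue, at little cost.

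**What to change.** Replace the primary outcome with a measured quantity: *the proportion of treated cases with clinical or histological recurrence, or worsening, by 5 years, with its 95% confidence interval*. State whether a case is a carcinoma or a participant. Remove the reference to all participants as a condition of cure. Use the same event definition in the per-case rule under Statistics, and keep the study-level success judgement only in that section.

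This is a change of protocol wording, with no added visits or data items. The sponsor gives up complete cure as the headline primary outcome. The change does not supply the missing margin for approximate equality, so the study-level rule stays open until that is set separately.

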### Study Objective

We seek to evaluate the effectiveness of fractional laser therapy and tirbanibulin ointment to treat squamous and basal cell carcinomas. We will execute this by using both thulium and erbium lasers on previously biopsy-confirmed SCCs and BCCs and applying bulk heating methods. Then, depending on the level of invasiveness, instruct subjects to apply the ointment over the course of five nights immediately following the treatment. The intention of this study

is to minimize the need for invasive surgical procedures so as to optimize the cosmetic appearance, and provide a treatment option that is beneficial for a wide range of individuals.

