**\*\*For nodular/invasive carcinomas:**

**-Night of Visit #1: At home ointment application to treated site**

**-Night #2- Night #5: At home ointment application to treated site**

-For approximately 10-14 days following completion of ointment application: At home wound care performed twice a day at the treated site. Patients instructed to complete wound care until site is completely healed (for some could take up to 1 month)

1 month post-tx: Follow-up to check site (Take biopsy per patient consent)

6 month post-tx: Follow-up for complete skin exam and to check site

1 year: Follow-up for complete skin exam and to check site (Take biopsy per patient consent)

1.5 year: Follow-up for complete skin exam and to check site

2 years: Follow-up for complete skin exam and to check site (Take biopsy per patient consent)

2.5 year: Follow-up for complete skin exam and to check site

3 year: Follow-up for complete skin exam and to check site (Take biopsy per patient consent)

3.5 year: Follow-up for complete skin exam and to check site

4 year: Follow-up for complete skin exam and to check site (Take biopsy per patient consent)

4.5 year: Follow-up for complete skin exam and to check site

5 year: Follow-up for complete skin exam and to check site (Take biopsy per patient consent)

\*\*Advise biannual skin exam thereafter (always recommended to any patients with history of SCC/BCC skin cancer)

\*\*Advise return to office ASAP if abnormalities occur at site at any point in time

**Patient recruitment:** Established patients will be recruited if they develop biopsy confirmed SCC or BCCs. They will be given the option to participate in the study. For new patients, recruitment will be based on referrals by current patients or other physicians. Additionally, new patients may be recruited through the office website, social media, or other online marketing conducted by employees of [name].

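### The study-level success rule ties no lesion type to its own recurrence benchmark, so an overall verdict of effective is compatible with one stratum, early or late, exceeding its benchmark

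*Protocol*

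**What the plan says.** **Regimen.** The Protocol's Study Objective states: "We seek to evaluate the effectiveness of fractional laser therapy and tirbanibulin ointment to treat squamous and basal cell carcinomas". All lesions receive laser. The ointment is conditional: "depending on the level of invasiveness, instruct subjects to apply the ointment over the course of five nights immediately following the treatment". In the schedule of visits the five-night course stands under the heading "For nodular/invasive carcinomas". That other lesions receive laser alone is implied, not stated.

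**Outcome.** The primary outcome is "Successful cure with the experimental method on all participants", against clinical recurrence or worsening. Secondary outcome 2 asks whether the method works in early but not in later stages.

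**Success rule.** The Statistics section states: "For the study as a whole, the treatment is considered effective if the recurrence rate is lower or approximately equal to the comparison groups". The comparison groups are the other approved or traditional treatments. It then cites five-year excision results: "superficial BCC recurrence rate is between 2% and 5%, nodular BCC 2-8%, SCC in situ ~0.8%, and invasive SCC between 1.7% and 6.4" (the last figure is also a percentage). It adds that electrodesiccation and curettage recurs more often, without a figure, and concludes: "we would consider our treatment successful if our recurrence rates are lower or approximately equal to any of the approved treatment options".

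**Subgroups.** "Subgroups will be defined by cancer type, cancer invasiveness, skin type, and gender". No success criterion is attached to any of them.

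**Eligibility.** Under Patient criteria, carcinomas of any invasiveness may enter, and so may certain hypertrophic actinic keratoses in which carcinoma cannot be ruled out. The Statistics section gives no benchmark for these keratoses.

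**The concern.** A single-arm study of a stage-adapted method is a legitimate design. The weakness is in how success is declared. The section sets out separate benchmarks for four lesion types, then states a rule that requires none of them to be met by the lesions concerned. Two features leave room:

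- The verdict is for the whole study and speaks of one recurrence rate, so a low rate in one lesion type can offset a high rate in another.
- The comparator may be any approved option, so a result worse than excision could still pass against a weaker method whose rate is not given.

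At stake is what the trial may conclude. The Study Objective names laser plus tirbanibulin as the treatment under evaluation. A pass driven by lesions not scheduled for the ointment could be published as evidence for the combination. The reverse can also happen: good results in nodular or invasive lesions could carry SCC in situ past its benchmark of about 0.8%. Under secondary outcome 2, stage and regimen also change together, so a difference between stages cannot be assigned to either one.

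**Working it through.** The 20 to 100 participants rest on office caseload, so the Protocol has no calculated figure to reproduce. The check asks how far one stratum can exceed its benchmark while a pooled rate still passes.

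**Inputs from the Statistics section:** SCC in situ about 0.8%; invasive SCC 1.7% to 6.4%; superficial BCC 2% to 5%; nodular BCC 2% to 8%.

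**Assumptions, not in the Protocol:** one lesion per participant; nodular/invasive share s of 20%, 50% or 80%; approximately equal read strictly as at or below the benchmark; pooling within one cancer type; the bar B for the pooled rate taken as the upper benchmark of the later-stage lesions.

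**Formula.** Pooled rate = (1 − s) × e + s × x, with e the early-stage rate and x the later-stage rate. The largest x that still passes is x = (B − (1 − s) × e) / s.

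**SCC, B = 6.4%, in situ at 0.8%:**
- s = 20%: (6.4 − 0.64) / 0.2 = 28.8%
- s = 50%: (6.4 − 0.40) / 0.5 = 12.0%
- s = 80%: (6.4 − 0.16) / 0.8 = 7.8%

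**BCC, B = 8%, same shares:**
- superficial at 2%: (8 − 1.6) / 0.2 = 32.0%; (8 − 1.0) / 0.5 = 14.0%; (8 − 0.4) / 0.8 = 9.5%
- superficial at 5%: (8 − 4.0) / 0.2 = 20.0%; (8 − 2.5) / 0.5 = 11.0%; (8 − 1.0) / 0.8 = 8.75%

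**The other direction, SCC.** With invasive SCC at 1.7%, the largest in situ rate that still passes 6.4% is (6.4 − s × 1.7) / (1 − s):
- s = 20%: (6.4 − 0.34) / 0.8 = 7.6%
- s = 50%: (6.4 − 0.85) / 0.5 = 11.1%
- s = 80%: (6.4 − 1.36) / 0.2 = 25.2%

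All exceed the in situ benchmark of about 0.8%.

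**How much depends on the bar.** If the pooled SCC rate were instead held to the benchmarks weighted by case mix, B would be 0.8 × 0.8 + 0.2 × 6.4 = 1.92% at s = 20%. With in situ at 0.8%, invasive SCC could then not exceed (1.92 − 0.64) / 0.2 = 6.4%. The Protocol states no such weighting.

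**Precision by stratum.** With zero recurrences in n lesions, the exact two-sided 95% upper limit is 1 − 0.025^(1/n): 60.2% for n = 4, 30.8% for 10, 16.8% for 20, 7.1% for 50 and 3.6% for 100.

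**The case against.** **Pooling is only one reading.** The Statistics section also uses the plural for its own rates and for the comparison groups, and lists benchmarks by type and stage. A stratum-by-stratum comparison may be what was meant. This stands as a point about intent. It does not supply a rule: nothing says that each stratum must meet its own figure, or that a failing stratum overrides an overall pass.

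**Failure in a stratum would be seen.** A reader might infer that the plan conceals poor results in later-stage lesions. It does not. Secondary outcome 2 asks that question, invasiveness is a subgroup, and invasiveness is recorded at the initial treatment. What is missing is any effect of these results on the verdict.

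**The word any.** A reader might infer that SCC in situ may be judged against the invasive SCC figure. The text does not support this: the word governs treatment options, and all four percentages belong to one option, excision. The room it opens is toward weaker methods such as electrodesiccation and curettage.

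**Only ointment-assigned lesions are at risk.** This too goes beyond the text, because the rule works in both directions.

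**Chance of conflicting verdicts.** Take a true invasive SCC rate of 12% (assumed), in situ at 0.8% and n = 100. The chance that the pooled SCC rate passes 6.4% while the observed invasive rate exceeds it is 68% at a 20% share and 40% at 50%. With the true invasive rate exactly at 6.4%, where there is no failure to mask, the same chances are 37% and 33%. Much of the apparent effect is therefore sampling noise, and the conclusion does not rest on it.

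**This belongs in the SAP.** Interval methods may well. The success rule, however, is stated in the Protocol, and a SAP that followed it would inherit the gap.

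**Conclusion.** The concern holds in limited form. As written, the rule permits an overall verdict of effective while a lesion type, early or late, recurs above its own stated benchmark. Secondary and subgroup results would show this but carry no criterion that alters the verdict.

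The possible size depends on case mix, which the Protocol does not give. In the SCC illustration the tolerated invasive rate is far above 6.4% when invasive lesions are a fifth of the sample and only slightly above it when they are four fifths. These are limits of what the rule allows, not forecasts. They assume pooling within a cancer type and the upper later-stage benchmark as the bar. They do not model the full mix of BCC, SCC and keratoses. If every stratum is at or below its benchmark, the pooled rule gives no wrong verdict.

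**What to change.** In the Statistics section, replace the comparison with any approved option by four comparisons: superficial BCC, nodular BCC, SCC in situ and invasive SCC, each against its own stated excision benchmark. In addition:

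- Report each rate with an exact 95% interval. Say in advance how the interval leads to a verdict, and give none where the stratum is too small for the interval to inform one.
- Report hypertrophic actinic keratoses separately, without a benchmark verdict.
- Label any pooled rate, including the primary outcome across all participants, as the result of the stage-adapted strategy. State which lesions receive ointment and, if meant, that the others receive laser alone.
- Limit claims about laser plus tirbanibulin to lesions given the ointment, and note under secondary outcome 2 that regimen and stage change together.

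**Cost.** No patient's treatment changes. The benchmarks are already in the Protocol, and invasiveness and treatment are already recorded. The price is precision. Splitting 100 lesions into two strata of 50 raises the zero-event upper limit from 3.6% to 7.1%, and splitting 20 into two of 10 raises it from 16.8% to 30.8%. At 20 to 100 participants over four strata, some will support no conclusion. For SCC in situ, even 100 lesions without a recurrence leave an upper limit well above 0.8%.

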**secondary**

1. The experimental method successfully treats one type of cancer but not the other (BCCs but not SCCs or vice versa)
2. The experimental method successfully treats early stages of the cancers, but not later stages (ex. Treats superficial SCCs but not invasive SCCs)
3. The experimental method successfully treats only specific parts of the body (ex. Treats areas of the body with thinner skin like the face, but not areas of thicker skin like on the back.)
4. The experimental trial method successfully treats only certain patients (differing results depending on age, skin type, ethnicity, etc).

**Data Collection/Data Management, Quality Control of Data**

-All data will be tracked by [name] and his medical assistants

-Detailed visit information, treatment and follow-up notes will be documented through the EMR program

Macpractice and we will utilize other data management methods such as google sheets

-Any missing data will be accordingly documented

-Missing data will be noted in results section/ likely to be reported in a table format

-Data will be collected at the initial treatment including patient demographics, location of lesion, invasiveness of carcinoma and treatment settings. Each subsequent follow up visit will include data in the format of “clinical recurrence or no clinical recurrence of carcinoma” at each follow-up visit. If a biopsy is taken and is clear then “no histological recurrence” will be reported. If the biopsy shows evidence of carcinoma, then the detailed pathological results will be reported. Any additional necessary data including complications will be tracked and reported.

-Written consent will be obtained by each patient prior to treatment and scanned electronically into their EMR patient file.

-Thermal data and images will be collected through TopDon thermal imaging camera application on an IPad, then exporting in graph form to google sheets.

